9 ETHICAL, LEGAL AND ADMINISTRATIVE ASPECTS

9.1 Data Quality Assurance

The Sponsor or Sponsor's designee will conduct a site visit to each study centre to verify the qualifications of each Investigator, inspect the site facilities and inform the Investigator of their responsibilities and the procedures for ensuring adequate and correct documentation.

The Investigator is required to prepare and maintain adequate and accurate case histories designed to record all observations and other data pertinent to the study for each study participant. All information recorded in the eCRF for this study must be consistent with the patients' source documentation (i.e., medical records).

9.1.1 Database Management and Quality Control

All study-related data generated by site personnel will be captured electronically at each study centre using the eCRF.

Central laboratory assays (e.g., PD) will be managed by the central laboratories and results will be transferred for inclusion in the study analysis database.

Once the eCRF clinical data have been submitted, corrections to the data fields will be captured in an audit trail. The reason for change, the name of the person who performed the change, and the time and date will be logged to provide an audit trail.

The specific procedures to be used for data entry and query resolution using the eCRF will be provided to study sites in eCRF completion instructions. In addition, site personnel will receive training on the eCRF. Once the source data verification is complete and all queries are closed, Data Management will freeze the eCRF page.

9.2 Case Report Forms and Source Documentation

All data obtained during this study must be promptly entered in the eCRF. All source documents from which eCRF entries are derived should be placed in the patient's medical records. Measurements for which source documents are usually available include laboratory assessments.

Data that will be entered directly into the eCRF (i.e., for which there is no prior written or electronic record) are considered source data.

The eCRF entries for each patient will be checked against source documents at the study site by the CRA.

9.2.1 Data Collection

The Investigators (and appropriately authorised staff) will be given access to an online web-based electronic data-capture system that is compliant with US Food and Drug Administration Title 21 Code of Federal Regulations Part 11. This system is specifically designed for the collection of clinical data in electronic format. Access rights to the electronic data-capture system will be carefully controlled and configured according to each individual's role throughout the study. Only the Investigator and authorised staff will be able to enter and correct data in the eCRF.

The eCRF should be completed for each patient included in the study and should reflect the latest observations on the patients participating in the study. Therefore, the eCRF is to be completed as soon as possible during or immediately after the patient's visit or assessment. The Investigator must verify that all data entries in the eCRF are

accurate and correct. If some assessments cannot be done, or if certain information is unavailable, not applicable or unknown, the Investigator should indicate this in the eCRF.

Computerised data-check programs and manual checks will identify any data discrepancies for resolution. Corresponding queries will be generated in the system and the site will be informed online about new issues to be resolved. All discrepancies must be resolved online directly by the Investigator or by staff authorised to do this by Delegation of Authority.

After completion, the Investigator will be required to electronically sign off the clinical data.

9.3 Access to Source Data

During the study, the CRO site CRA will make regular site visits to review protocol compliance, conduct source data verification by comparing eCRF entries and individual patient's medical records, assess drug accountability and management, assess laboratory procedures and ensure that the study is being conducted according to pertinent regulatory and protocol requirements. The review of medical records will be performed in a manner that ensures patient confidentiality is maintained.

Source data verification will be required to monitor the progress of the study. Moreover, regulatory authority, IECs and/or the Sponsor's Clinical Quality Assurance Group or designee may wish to carry out such source data checks and/or on-site audit inspections. Direct access to source data will be required for these inspections and audits; they will be carried out giving due consideration to data protection and medical confidentiality. The Investigator must assure the CRO and the Sponsor that they will provide the necessary support at all times.

9.4 Archiving Study Records

According to ICH guidelines, essential documents should be retained for a minimum of 2 years after the last approval of a marketing application in an ICH region and until there are no pending or contemplated marketing applications in an ICH region or at least 2 years have elapsed since the formal discontinuation of clinical development of the investigational product. However, these documents should be retained for a longer period if required by the applicable legal requirements. For example, in Finland data needs to be stored at least for 15 years.

9.5 Good Clinical Practice

The procedures set out in this study protocol are designed to ensure that the Sponsor and Investigator abide by the principles of the Good Clinical Practice guidelines of the ICH and the Declaration of Helsinki. (Declaration of Helsinki 2013) The study will also be carried out in keeping with local legal requirements.

9.6 Informed Consent

The Investigator at each investigational site is responsible for ensuring that informed consent (written signed or witnessed) for study participation is given by each patient prior to collection of study data and administration of the study drug. The informed consent should be sought from the patient, but due to emergency nature of the condition it may be in the best interest of the patient to move straight on for surgery

and an adequate amount of time cannot be spent on consenting. This will be determined by the investigator in the best interest of the patient. In such a case the investigator can seek informed consent from the next of kin during a four-hour time period when the patient moves from the OR to the ICU and the drug must be administered.

If consent has not been obtained, a patient cannot be randomised into the study.

If a protocol amendment is required, the ICD may need to be revised to reflect those changes. If the ICD is revised, it must be reviewed and approved by the appropriate IEC, and signed by all patients (or their representatives) subsequently enrolled in the study as well as those currently enrolled in the study.

9.6.1. Consent Procedure

Informed consent must be obtained from the patient. The patient is informed about the study by the Principal Investigator or by a member of the research team to whom the Principal Investigator has allowed delegation of the consent process.

The patient is given a copy of the Patient Informed Consent Document (PICD). Informed patients are given an adequate amount of time to consider their decision about entering the study. However, the requirement to initiate surgery can significantly limit the amount of time available and the operating vascular surgeon will determine the time that may be used for this, as considered best for the patient.

If a patient decides to enter the study he or she is asked to sign the consent. If the patient is unable to sign the consent document due to ongoing preparations for operation or e.g. stomach pain, or any other relevant reason, and inability to sit up for signing, a verbal consent can be given with a witness of one members of medical staff excluding the study personnel. The consent document is then countersigned by a member of the study team to whom obtaining of consent has been delegated. One copy of the document is retained by the patient. Another copy is placed in the patient's medical records (only if it is required locally). The original document is retained in the Investigator Site File.

If there is not adequate time to consent the patient prior to surgery, but otherwise the patient would be eligible for the study (complete unconsciousness leads to exclusion), the investigator can seek consent from the next of kin after the surgery. If this approach is taken written informed consent needs to be taken from the study subject at the soonest possible moment.

9.6.2. Withdrawal of Consent

Patients may withdraw from the study at any time, for any reason and such a decision will not affect standard care given to the patient. Data recorded up to the point of withdrawal is included in the study analysis.

If a patient requests termination of the administration of study medication during the treatment period, the administration of study medication is terminated but the patient will continue in the study and all follow-up assessments are performed.

If a patient withdraws consent during the treatment period, the administration of study medication is terminated and no further active study assessments are performed from that point on. However, permission will be sought to access the patient's medical records for data relevant to the study (e.g., mortality, Ventilator Free Days [VFDs] etc.) and the patient will be asked to complete the D30 physical follow up.

If a patient withdraws consent after the treatment period then no further active study assessments will be performed from that point on. However, permission will be sought to access the patient's medical records for data relevant to the study (e.g., mortality, VFDs, etc.) and the patient will be asked to complete the D30 physical follow up.

9.7. Protocol Approval and Amendment

For the study to start, all required documentation must be approved by the IEC and Competent Authority, in accordance with local legal requirements. The Sponsor must ensure that all ethical and legal requirements have been met before the first patient is enrolled in the study.

This protocol is to be followed exactly. To alter the protocol, amendments must be written, receive approval from the appropriate personnel, and receive IEC/competent authority approval prior to an implementation (if appropriate).

Administrative changes (not affecting the patient benefit/risk ratio) may be made without the need for a formal amendment. All amendments will be distributed to all protocol recipients, with appropriate instructions.

9.8. Independent Data Monitoring Committee

An IDMC will be established for the study. The duty of the committee is to protect ethical and safety interests of patients and all others who may possibly be exposed to the study medication and to make recommendations to the investigators. The IDMC will review safety data retrieved for interim analysis (i.e. AEs and SAEs) in an unblinded manner and will give recommendations to the Sponsor regarding study modification and/or termination. The IDMC will comprise at least three members, including at least one independent biostatistician and two clinicians not otherwise involved in the study.

An IDMC charter is established, which documents in more detail the responsibilities, duties and objectives of the individuals and of the committee.

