Interim Analyses:

Interim analysis will be performed after there are at least 31 and 84 evaluable patients for the primary efficacy endpoint analysis. At this point the study can be stopped for efficacy or futility depending on the interim analysis results. The first interim is brought further up as the recruitment rate has markedly stagnated, mainly due to changes in treatment practices of RAAA. The sample size calculations will be re-evaluated after the first interim analysis.

**Independent data
monitoring committee
(IDMC)**

IDMC consist of key opinion leaders in scientific field and is responsible for overlooking the overall safety of the study. IDMC is obliged to discontinue the study, if the benefit risk balance is negative.

LIST OF STUDY PERSONNEL

Sponsor [REDACTED]
Faron Pharmaceuticals Ltd
[name]
[name], Finland
[REDACTED]
[REDACTED]

Co-ordinating Investigators [REDACTED]
[REDACTED]

Contract Research Organisation [REDACTED]
[REDACTED]

Safety Reporting [REDACTED]
[REDACTED]
[REDACTED]
[REDACTED]

Central Laboratory for Analysis of Neutralising Antibodies to IFN beta-1a, MxA and CD73 [REDACTED]
[REDACTED]
[REDACTED]

Central Laboratory for Analysis of HGF and IL-6 [REDACTED]
[REDACTED]
[REDACTED]
[REDACTED]

Drug Supply

[REDACTED]

[REDACTED]

[REDACTED]

[REDACTED]

[REDACTED]

[REDACTED]

[REDACTED]

[REDACTED]

**Data Management and
Statistical Analyses**

[REDACTED]

[REDACTED]

[REDACTED]

TABLE OF CONTENTS

PROTOCOL SYNOPSIS	6
LIST OF STUDY PERSONNEL.....	12
LIST OF ABBREVIATIONS AND DEFINITIONS OF TERMS	17
1 INTRODUCTION	19
1.1 DISEASE REVIEW AND RATIONALE FOR THE STUDY	19
1.2 INVESTIGATIONAL MEDICINAL PRODUCT	20
1.3 MECHANISM OF ACTION	20
1.4 PRECLINICAL AND CLINICAL DATA	21
2 STUDY OBJECTIVES	22
2.1 PRIMARY OBJECTIVE.....	22
2.2 SECONDARY OBJECTIVES	22
3 OVERALL DESIGN AND PLAN OF THE STUDY.....	23
3.1 SUMMARY OF STUDY DESIGN.....	23
3.2 CRITERIA FOR THE STUDY ASSESSMENTS.....	25
3.2.1 Primary Efficacy Endpoint:	25
3.2.2 Safety	25
3.2.3 Pharmacoeconomics assessments	25
3.2.4 Exploratory endpoints assessments	25
3.3 JUSTIFICATION OF THE STUDY DESIGN.....	26
4 STUDY POPULATION.....	27
4.1 INCLUSION CRITERIA.....	27
4.2 EXCLUSION CRITERIA	27
4.3 CONFIRMATION OF PATIENT ELIGIBILITY.....	28
4.4 PATIENT WITHDRAWAL AND REPLACEMENT	28
4.4.1 Discontinuation Criteria	28
4.4.2 Replacement Policy	30
4.5 PLANNED SAMPLE SIZE AND NUMBER OF STUDY CENTRES	30
4.6 PATIENT RANDOMISATION	30

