3 OVERALL DESIGN AND PLAN OF THE STUDY

3.1 Summary of Study Design

This is a multicentre, randomised, double-blind, Phase II, parallel group comparison study of the efficacy and safety of FP-1201-lyo compared to placebo in patients surviving emergency open surgery for an infra-renal ruptured abdominal aortic aneurysm. Both treatment groups will receive standard supportive care.

With an estimated screening failure rate of approximately 15%, maximum of 180 patients will be consented and entered into the study in order to randomise and initiate treatment of 152 patients. The sample size calculations will be re-evaluated after the first interim analysis has been performed.

The study design incorporates an Independent Data Monitoring Committee (IDMC) that will review safety data retrieved for interim analysis (i.e. Adverse Events [AE] and Serious Adverse Events [SAE]). Details of the IDMC are given in Section 9.8.

[figure not shown]
Patients will receive 10 µg FP-1201-lyo or placebo intravenously as a bolus injection once every 24 hours. The maximum duration of treatment will be 6 days. Treatment may be discontinued before 6 days if the patient's condition improves beyond the need for ICU treatment and if, in the opinion of the Investigator, the patient would likely not benefit from continuation of treatment.

A schedule for the tests and assessments to be conducted during this study is found in the Tables 5-8.

The study objectives and outcome measures to be used in this study are described in Sections 2 and 6.

The study design is summarised below in Figure 1.

Figure 1: Flow Diagram of Study Design

3.2 **Criteria for the Study assessments**

3.2.1 **Primary Efficacy Endpoint:**

- All-cause mortality at D30

Secondary Efficacy Endpoints:

- All-cause mortality at D90 (3 months)
- Number of ventilator free days (VFDs) at D30
- Number of days receiving hemodialysis at D30 and D90
- Number of organ failure free days up to D30 by means of the SOFA score
- Prevalence of abdominal compartment syndrome, i.e. intra-abdominal pressure (IAP) between study groups
- Neutralizing antibodies against IFN beta-1a (NAbs) in whole blood samples up to D30
- Disability at D90 (3 months) by modified ranking scale.

3.2.2 **Safety**

- Clinically significant treatment emergent adverse events (TEAEs) up to D30 from vital signs data, laboratory data, physical examinations and spontaneous reporting when conscious

3.2.3 **Pharmacoeconomics assessments**

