4.4 Patient Withdrawal and Replacement

4.4.1 Discontinuation Criteria

Patients may discontinue from the entire study, including follow-up, at any time without any reason and without prejudice to their future medical care; they are not obliged to state their reasons for withdrawing.

Additionally, the Investigator may discontinue a patient at any time if it is considered to be in the best interest of the patient. Discontinuation of study medication by the Investigator due to improvement of a patient's condition **does not** constitute a withdrawal as the patient will continue with the study assessments.

A patient **may be discontinued** from the study for example of the following reasons:

- Protocol violations including non-compliance with study procedures or patient lost to follow-up
- SAEs
- Administrative reasons
- Patient request
- Sponsor request
- Investigator request
- Authority request

In the case of a discontinuation, the Investigator must ensure that the status page in the eCRF for the **end of the study** is completed.

Patients may be required to **discontinue from study drug** after discussion with the Sponsor and/or Investigator for the following reasons:

- AEs
- At the discretion of the Investigator or if it is considered to be in the patient's best interest

If the administration of study medication is prematurely discontinued, the primary reason for discontinuation must be recorded in the appropriate section of the eCRF and all efforts made to complete the observations on that study treatment day as thoroughly as possible.

A complete final evaluation following the patient's discontinuation should be made on the day of the discontinuation/discharge, as described in Section 7.2. and any ongoing AEs should be followed up to resolution or study D30, whichever occurs first.

The study will be terminated if, in the opinion of the Sponsor, significant safety concerns arise during the conduct of the study.

Patients who discontinue study drug may continue in the study. The Investigator must ensure that the status page in the eCRF for the end of study is completed.

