5.4 Blinding and Breaking the Blind

The study will be performed in a double-blind manner. All study drugs will be supplied in identical vials and will be similar in colour and appearance, thereby enabling double-blind conditions.

The treating physician (investigator) is responsible for the medical care of the trial patient and the study set up allows the investigator to rapidly break the treatment code in case of an emergency.

The study blind should only be broken in a medical emergency (where knowledge of the study drug received would affect the treatment of the emergency) or as a regulatory requirement (e.g., for SAEs or death). Note that there is no specific antidote or method of removing the study drug from the body (such as dialysis) and the best available care for the patient should be continued.

If the blind is broken, the date, time and reason must be recorded in the patient's eCRF and any associated AE report. It is the responsibility of the investigator to promptly document and explain any unblinding to the sponsor/CRO.

Detailed instructions for the use of the IWRS in order to break the study blind for a patient are provided in a separate document that will be filed in the Site File and Trial Master File. As well as the IWRS, a backup system enabling unblinding of treatment is provided to the sites.

After a patient has been unblinded data collection should continue as per protocol.

Suspected unexpected serious adverse reactions (SUSARs), which are subject to expedited reporting, should be unblinded before submission to the regulatory authorities and Independent Ethics Committees (IECs).

The overall randomisation code will be broken only for reporting purposes (for interim and final analyses). This will occur once all D90 clinical data have been entered into the database and all data queries have been resolved, and the assignment of patients to the analysis sets has been completed. The randomisation code will be opened for the interim analysis, which is performed when at least 31 patients have been enrolled and the D30 clinical data is available.

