5.8 Guidance on medications to be administered/patient management for expected Adverse Events

Recombinant Human IFN beta-1a has been widely used in man for the treatment of multiple sclerosis and is considered safe. Some adverse effects are anticipated. Most common are changes in blood biochemistry of liver function, i.e. ALAT, ASAT, AFOS. A slight elevation in liver enzymes is often seen, and needs to be followed. These changes usually subside after cessation of treatment. Most common severe adverse effects are fever, tachycardia and rigor, since the drug substance is to some extent pyrogenic by nature. These adverse effects mostly occur shortly after administration and cease after treatment. These adverse effects may be managed with otherwise suitable medication depending on the symptom: paracetamol or other antipyretics for fever, beta blockers for tachycardia, benzodiazepines for rigor or even propofol sedation in the ICU setting.

Few adverse effects are expected after the treatment period since, as shown in the FPCLI001 study, FP-1201 activity decreases significantly within few days after administration, according to MxA measurements. Thus, the IMP will be washed out before discharge from the hospital. For more information on the anticipated effects of the FP-1201-lyo treatment see the **Investigators' Brochure**.

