8.6 INTERIM ANALYSIS

An interim analysis will be performed after there are 1) at least 31 and 2) 84 patients that are eligible for the primary efficacy endpoint analysis (excluding early deaths within 36 hours from first dose of study treatment, similarly than for primary analysis). At this point the study can be stopped for efficacy or futility depending on the interim analysis results. The first interim is brought further up as the recruitment rate has markedly stagnated, mainly due to changes in treatment practices of RAAA. The sample size calculations will be re-evaluated after the first interim.

Primary efficacy endpoint will be evaluated using O'Brien and Fleming criteria controlling the type I error rate. If the study goal is reached, the study can be stopped early for efficacy. The first interim analysis focuses mainly for the futility stopping, as the power is low to reach the efficacy criteria. The power to reach the study goal at the second interim analysis with 84 evaluable patients is approximately 40%, but also this calculation will be re-evaluated after the first interim.

In addition, there will possibility to stop the study for futility at the interim analyses. Predefined criteria for futility stopping will be defined in the interim analysis plan.

Statistical analysis plan for the final and interim analysis will be prepared before the interim analysis. A blind review of data will be performed before the interim analysis to confirm analysis assumptions for e.g. overall number of events.

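### The only unblinded IDMC safety reviews scheduled in the protocol or SAP are tied to interims counted in patients who survive 36 hours, so the first comparison of arms is late and early deaths push it modestly later

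*Protocol*

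**What the plan says.** **What the IDMC reviews.** Protocol 9.8: "The IDMC will review safety data retrieved for interim analysis (i.e. AEs and SAEs) in an unblinded manner". Section 3.1 ties the review to the interim data in the same way. Section 9.8 refers to a charter for further detail; it is not among the documents.

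**When the interims fall.** Protocol 8.6 places them "after there are 1) at least 31 and 2) 84 patients that are eligible for the primary efficacy endpoint analysis", and specifies "excluding early deaths within 36 hours from first dose of study treatment, similarly than for primary analysis". SAP 9.5 counts in the same unit but gives 35 and 84. Protocol 5.4 times the first unblinding differently: "which is performed when at least 31 patients have been enrolled and the D30 clinical data is available".

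**What can stop the study.** Section 8.6 gives efficacy and futility as the interim stopping reasons, with the futility criteria left to a separate interim analysis plan. More general clauses allow a safety stop:
- Synopsis: "IDMC is obliged to discontinue the study, if the benefit risk balance is negative".
- Section 4.4.1: "The study will be terminated if, in the opinion of the Sponsor, significant safety concerns arise during the conduct of the study". A later sentence there names the IDMC or the Sponsor.
- Section 9.9: the Sponsor may stop at any time.
- Section 9.8: the IDMC gives recommendations to the Sponsor.

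**Where early deaths are counted.** Protocol 8.1 and SAP 8 exclude them from FAS-E but keep them in FAS-S. SAP 8 states that the first interim was based on FAS-E. In SAP 19.3 the main D30 and D90 mortality tables are labelled FAS-E or PPS, and no table is planned that compares deaths within 36 hours by arm.

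**The concern.** A safety review should come no later when more patients die early on treatment. Here the review clock advances only with patients who live 36 hours, so each early death has to be made up by another treated patient before the IDMC sees unblinded data.

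The window matters on the protocol's own account. Section 8.5.1 argues that therapeutic levels are not reached before 36 hours, so these hours carry exposure without expected benefit. Section 5.8 says of fever, tachycardia and rigor: "These adverse effects mostly occur shortly after administration and cease after treatment".

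Review of single SAEs, due within 24 hours under section 6.3.1.5, does not replace a comparison of arms. About 15% of these patients are expected to die early in any case, so each death has a ready explanation in the disease. What is at stake is how many patients are treated before anyone compares the arms.

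**Working it through.** **Inputs.** Evaluable patients at the looks: 31 and 84 (protocol 8.6), or 35 and 84 (SAP 9.5). Early deaths: 15%, not split by arm (protocol 8.2). Allocation 2:1. Evaluable total 129, randomised 152. The early-death rates by arm used below are assumptions.

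**1. The plan's own inflation.** 129 / (1 − 0.15) = 151.8, so 152. This reproduces the stated figure, and the same formula converts each look into treated patients.

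**2. Looks with no excess of early deaths.**
- 31 / 0.85 = 36.5, so 37 treated (37/152 = 24% of the trial).
- 35 / 0.85 = 41.2, so 42 treated.
- 84 / 0.85 = 98.8, so 99 treated (99/152 = 65%).

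On the section 5.4 wording, D30 data must also be in hand at the first look. Patients treated during that wait come on top. The documents give no recruitment rate, so I do not put a number on them. No review is scheduled between the second look and the final analysis.

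**3. Looks with an excess on active.** Hold placebo at 15%. Pooled rate = (2 × active rate + 0.15) / 3, and treated = evaluable / (1 − pooled rate).

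| Active early deaths (assumed) | Pooled | 31 evaluable | 35 evaluable | 84 evaluable |
|---|---|---|---|---|
| 15% | 15.0% | 37 | 42 | 99 |
| 20% | 18.3% | 38 | 43 | 103 |
| 25% | 21.7% | 40 | 45 | 108 |
| 30% | 25.0% | 42 | 47 | 112 |
| 40% | 31.7% | 46 | 52 | 123 |

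If early deaths on active double to 30%, the delay is 42 − 37 = 5 patients at the first look and 112 − 99 = 13 at the second.

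**4. Early deaths accrued by then, at 30% versus 15%.**
- First look (31 / 0.75 = 41.3 treated): active 2/3 × 41.3 × 0.30 = 8.3; placebo 1/3 × 41.3 × 0.15 = 2.1.
- Second look (112 treated): active 2/3 × 112 × 0.30 = 22.4; placebo 1/3 × 112 × 0.15 = 5.6.

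None of these deaths enters the interim efficacy statistic; all of them are in FAS-S.

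**5. The two counting rules side by side.** If enrolled in section 5.4 means treated, 31 such patients would give about 31 × 0.85 = 26 evaluable, short of the 31 in section 8.6. On the 5.4 wording early deaths would not delay the first look; on the 8.6 wording they would. The two sections describe different moments.

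**The case against.** **The charter is unseen.** Section 9.8 says it sets out the IDMC's duties in more detail, so it may hold further reviews or a way to call an ad hoc meeting. A reader might infer that no such rule exists. The documents support only that none is stated in the protocol or SAP.

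**A safety stop is available at any time.** The synopsis and sections 4.4.1 and 9.9 allow it. This stands against any claim that the trial could not stop for harm. But these clauses schedule no unblinded comparison on which to act.

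**Early deaths are not hidden.** A reader might infer that excluding them from FAS-E keeps them from the IDMC. It does not: they are in FAS-S, and the IDMC sees SAEs unblinded once it meets. The point is about when it meets.

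**The delay is small and conditional.** It is 5 patients at the first look if early deaths on active double, and none on the section 5.4 wording. Nothing in the documents says that the drug causes early death, and section 5.8 describes its expected reactions as manageable. This stands; the rates above are illustrations.

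**The efficacy boundary is not the harm rule.** A reader might judge protection against harm by the chance of crossing the O'Brien-Fleming boundary in the wrong direction. Section 8.6 says the first interim is mainly for futility, and those criteria are in a plan not available here, so that calculation would say little.

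**Authority.** The statements in 4.4.1 and 9.9 are compatible with each other. The conflict that remains is between the synopsis, which obliges the IDMC to discontinue the study, and 9.8, under which it recommends.

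**Conclusion.** The point holds as one about scheduling. On the text of the protocol and SAP, the first unblinded comparison of arms for safety comes at about 37 treated patients plus D30 follow-up (42 if 35 evaluable are needed), and the second at about 99. That gap exists with no drug harm at all and is the larger part of the problem. Counting in 36-hour survivors adds a modest delay in the wrong direction: 5 and 13 patients at an assumed 30% versus 15%.

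The result rests on the planned 15% early-death rate, 2:1 allocation among treated patients, the section 8.6 count, and a charter that adds nothing. If the charter already schedules earlier reviews, citing it would settle that part. The SAP reports that the study was discontinued after the first interim, so only the first look took place. For this trial the remaining use is in the report; the scheduling lesson applies to any similar protocol.

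**What to change.** 1. In section 9.8, time the IDMC's unblinded safety reviews by the number of treated patients (FAS-S), separately from the efficacy interims and without waiting for D30 data.
2. Require each closed report to show, by arm in FAS-S, deaths within 36 hours of the first dose and all deaths. As the study has stopped, the same table can be added to the final report.
3. State, or cite from the charter, how an ad hoc review is convened. Leave the threshold to the IDMC.
4. Reconcile enrolled (5.4) with eligible (8.6); 31 (protocol) with 35 (SAP 9.5), noting that 35 does satisfy the protocol's minimum of 31; and the IDMC's obligation to discontinue (synopsis) with its recommending role (9.8).

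**Cost.** Protocol and charter wording, a short closed table, and possibly one or more extra meetings. No efficacy alpha is spent if these reviews can stop the study only for harm.

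A numerical trigger would bring false alarms. As an illustration, take a one-sided Fisher p<0.10 on early deaths or on total deaths, at 36, 60 and 100 treated. With no drug effect (15% early and 37% later mortality in both arms, D30 totals assumed known), simulation gives at least one alarm in about 19% of trials: about 9% for early deaths alone and 13% for total deaths alone. Its yield is limited too: at 30% versus 15%, the early-death part fires at 36 treated about 22% of the time and at 60 about 37%. That is why the threshold, and whether to have one, is better left to the committee.
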